### Waiver of Consent/Authorization

Indicate if you are requesting any of the following consent waivers
Waiver of consent for use of records that include protected health information (a HIPAA waiver of Authorization)

No

Waiver or alteration of consent

No

Waiver of documentation of consent

No

Waiver of parental consent

No

### **Consent Procedures**

Is eligibility screening for this study conducted under a different IRB protocol? Yes
Indicate NYSPI IRB #
6879R and 4815
Describe Study Consent Procedures

- 1. Possible participants will complete an initial phone screen with a research coordinator after providing verbal consent, through screening protocol #6879R.
- 2. Potentially eligible participants are scheduled for an evaluation and consent session. There, participants are given a detailed verbal explanation of screening procedures by a research staff member. Participants then give written informed consent for screening procedures (under screening protocol #6879R).
- 3. If eligible, based on #6879R screening, participants will be asked to sign the consent form for IRB protocol #4815 (Biological and Neuropsychological Measures for Genetic Studies of Psychiatric Populations—PI: [name]). Participants will then be given **laboratory** (blood draw) and psychiatric examinations, performed under protocol #4815.
- 4. Participants will also be given a detailed verbal explanation of this study by a research MD and then will give written informed consent, if they choose to participate in the study. Subjects who are

unable to come to NYSPI for multiple visits will complete consenting via NYSPI-approved remote platforms including Webex, Zoom, or telephone. The commonest reason is that they live too far away and may fly in or take a train a long distance to participate in the study. We want to be as sure as possible they are both eligible and willing to participate before they travel a long way to come to our center.

- 5. A Note to File will be added to the participant's charts that documents screening and study consent discussions, signed by the consenter and dated on the day of the consent discussions.
- 6. Consent discussions will include informing participants of the option to reschedule if travel does not seem safe and/or the study team may offer alternative transportation, such as Uber or Lyft.
- 7. There will be a consent procedure note that includes that there was a discussion of risk related to COVID-19 during travel.

All screening and consenting procedures will be done remotely over a HIPAA-compliant videoconferencing software (Webex or Zoom) or telephone. We will document consent for remote clinical or research procedures, the consent discussion process will include discussion of the technology HIPAA-compliant platforms to be used and any concerns the patient may have, such as access to a private space in which to take calls, or accessibility—access at home to adequate devices, cell signal, or wifi.

We will use REDCap with e-signature function enabled to obtain electronic documentation of consent.

Indicate which of the following are employed as a part of screening or main study consent procedures

- ✓ Consent Form
- ✓ Information Sheet

# **Independent Assessment of Capacity**

You have indicated that your study involves subjects who MAY LACK capacity to consent. Does this study require an independent assessment of capacity?

No

# **Study Procedures**

Describe the procedures required for this study

I attest to follow the COVID-19 Safety Guidelines for Columbia Psychiatry and NYSPI Re-Entry outlined in the NYSPI Director's June 1st memo, which include but are not limited to:

- Infection Control/PPE Guidelines
- Research participants will only come on-site if absolutely necessary for study procedures.
- No volunteers/externs on-site during Stage 1.
- Clinical research teams will screen their participants for COVID symptoms (night before and day of onsite visit, documenting this in the chart), and escort them in and out of the building.
- COVID/COVID-like symptoms in participants will be reported to the IRB via PRISM as an SAE.
- All inpatient participants will be tested for COVID and will be determined negative for COVID prior to admission on 5 South. Testing will occur either in the ER, through an outside private laboratory or via NKI. In the latter two cases, nasal swabbing may be performed at NYSPI by trained staff and sent to these laboratories. Alternatively, COVID testing may be performed via saliva sample. COVID testing will be repeated upon admission to the inpatient unit, and within 48 hours of discharge.

### **Procedures**

### 1. Screening

- a. We will recruit inpatients or outpatients with MDD in a major depressive episode. Referrals generally come from physicians, clinics, the NYPH Emergency Department, and ads in media including the internet.
- b. Participant completes phone screen, approved under IRB #6879R (which may be done inperson if in the emergency room or on an inpatient unit). If participant appears eligible based on the phone screen, they will be scheduled for a more in-depth screening visit under Screening Protocol (IRB #6879R) to determine whether inclusion/exclusion criteria (excluding medical screening) are met. Screening will occur via NYSPI-approved remote platforms including Webex, Zoom, or telephone.
- c. Secure video/phone interviews: Under the procedures described in protocols #4815 and #6879R, consent forms for this protocol will be sent to the subject to be reviewed with an approved consenter at the end of the eligibility screening. Subjects will be asked to print the form prior to their eligibility screening.
- d. Secure video/phone interviews: Following the interview conducted under #6879R, the consenter will review the consent form for this protocol that was emailed to the subject. Consent forms will be signed electronically by the participant and the consenter in RedCap.
- e. Secure video/phone interviews: Following the procedures detailed in protocol #4815, if the consenter determines that the potential subject has suffered a serious head injury a trailmaking test (TMT) will be sent to the subject. Research staff will administer the test over secure video as described fully in protocol #4815.
- f. For in-person screening procedures (which may be used with patients in the emergency room or on an inpatient unit), participant is given a detailed, verbal explanation of this study and IRB #4815 and given a copy of both consent forms.

- g. Participant gives written informed consent to participate in IRB #4815 and this study.
- h. Participant receives medical evaluation under IRB #4815. Genetics blood sample is also acquired under IRB #4815 (Biological and neuropsychological measures for genetic studies of psychiatric populations—PI: [name]).
- i. An electrocardiogram will be performed to evaluate any cardiovascular contraindications to research procedures.
- j. Final eligibility is determined when results of laboratory tests acquired through IRB #4815 are obtained.
- k. During the period between enrollment and the infusion, the treating physician will assess the patient weekly in by phone, through secure video, or in person if these options are not available, through a clinical interview and a Clinical Global Impression (CGI) scale. If concerns are noted during a telephone or secure video contact, participants may be brought in for an in-person visit. If a participant has a CGI-I >5 at any time, the treating psychiatrist will assess whether it is safe to continue research participation and will discuss with the participant the possibility of discontinuing research procedures and initiating open clinical treatment.

If after enrollment a subject refuses inpatient admission that is deemed clinically necessary by the research team they will be withdrawn from research.

### 2. Prior Psychiatric Medication

a. For insomnia or anxiety, PRN diphenhydramine, hydroxyzine, zolpidem, or a benzodiazepine will be permitted. The goal will be the equivalent of a maximum daily dose of lorazepam ≤2mg during the week leading to the first infusion. However, no zolpidem, eszopiclone, zaleplon, or benzodiazepine will be permitted during the 72 hours pre-infusion and during the 72 hours prior to PET imaging. Subjects who at enrollment are taking a higher equivalent benzodiazepine dose will be tapered and converted to lorazepam during the pre-infusion week. Subjects who show signs of benzodiazepine withdrawal or who cannot tolerate the 24-hours without zolpidem, eszopiclone, zaleplon, or benzodiazepine will be withdrawn from the protocol. b. Current psychiatric medications other than benzodiazepines or the above sleep medications will be maintained at a stable dose until post-infusion treatment. Minor dose adjustments may be made pre-infusion, such as to reduce side effects.

### 3. Actively Suicidal Patients

- a. Patients with imminent (next few days) suicidal plan or intent will only be enrolled if they agree to acute inpatient hospitalization. The independent treatment team on the inpatient research unit must agree that study participation is clinically reasonable.
- b. For patients who require hospitalization because of destabilization or suicidal risk, admission to a NYSPI unit will be available. Hospitalized patients will be discharged from the

hospital when stable as judged by the inpatient staff and the treating psychiatrist as not being in imminent risk of harm to self/other.

c. A research psychiatrist will be available by telephone 24 hours a day, seven days a week. Patients requiring urgent admission will be brought to the NewYork Presbyterian/Columbia University Irving Medical Center Emergency Room by the study physician with security assistance, if needed. Non-emergent admissions will be arranged by the treating psychiatrist, if possible to 5 South or 4 Center. Patients who are deemed to require hospitalization, but who refuse hospitalization, will receive all necessary interventions such as contacting the local crisis team, family, or Emergency Medical Services.

### 4. Inpatient Phase.

a. To participate in the study, patients must agree to inpatient hospitalization at NYSPI (4 Center or 5 South units) throughout the period in which the following procedures occur: baseline neuroimaging (MRI and PET), ketamine infusions, and post-ketamine imaging (PET). Our goal will be for the admission to be as short as possible, but in general we anticipate that it may be on the order of 21 days, or more if clinically indicated. Patients will be evaluated by a research physician and the inpatient unit's independent clinical team and will be discharged when assessed, according to standard practice, as safe for outpatient treatment in the research clinic. Patients who need to be kept involuntarily for safety reasons will be withdrawn from research and treated clinically.

### 5. Pre-Infusion Research Measures

- a. Baseline clinical and neuropsychological ratings (See Figure 1, attached); may be performed as inpatient or outpatient.
- b. Baseline MRI imaging will take place at the New York State Psychiatric Institute on a GE SIGNA Premier 3T MRI Scanner, generally on a day prior to ketamine infusion, although it may take place after the ketamine infusion if scheduling constraints make this preferable. MR imaging will include T1-weighted structural MRI of the brain for coregistration to PET and identification of regions of interest. Resting-state functional MRI and diffusion weighted imaging acquisitions may be performed if time allows. MRI scanning time will not exceed 30 minutes. Scanning at NYSPI will occur on the GE Signa Premier 3T MRI system. A urine pregnancy test will be performed on women of child-bearing potential on the day of the MRI scan. Inpatients will be accompanied to the MRI Center by a research staff member (coordinator, psychologist or psychiatrist) who will remain in the MRI Center throughout the scan and bring them back to the inpatient unit at the completion of the scan.
- c. Before the MRI occurs, participants will have the option of visiting the MRI suite and entering a mock MRI scanner. The mock scanner is identical in size to an MRI scanner but cannot take pictures of the brain. Trying out the mock MRI scanner simulation gives participants an idea of what the MRI scan will be like and may reduce their anxiety about the scan.

- d. Baseline PET imaging will be performed at the Columbia PET Center prior to the first ketamine infusion, within one week prior to the first ketamine infusion; this could include scanning on the day of ketamine infusion itself prior to the infusion. PET imaging will be performed at the Columbia PET Center. SV2A will be quantified via PET with [¹¹C]UCB-J, synthesized as previously described (17). Radiotracer synthesis will occur in the radioligand laboratory at the Columbia PET Center. Baseline PET scanning will occur within one week prior to ketamine infusion. After acquisition of a low dose CT scan for attenuation correction, [¹¹C]UCB-J will be injected as an intravenous bolus (≤740mBq), and PET data acquired on a Siemens mCT Biograph over 90 minutes. A urine pregnancy test will be performed on women of child-bearing potential on the day of each PET scan.
- e. Blood Analysis: A radial artery catheter will be placed prior to PET imaging for concurrent blood sampling to measure arterial input function and unmetabolized plasma fraction of [C]UCB-J using high-performance liquid chromatography. The radial artery catheter will be placed by a physician after completion of the Allen test and infiltration of the skin with 1% lidocaine. If a participant has a known allergy to lidocaine, an alternative local anesthetic may be used. Blood samples will be drawn using a combination of automated and/or manual blood sampling during the course of the PET scan. No more than 100 ml of blood will be drawn for this purpose at each of the two PET scans. In the event that a radial artery catheter cannot be placed, we may place a second intravenous catheter and perform venous blood sampling instead of arterial blood sampling.
- f. After the scan is over, the participant exits the camera, the arterial and venous lines are removed, and discharge from the PET Center will be contingent upon clearance by the clinical and research staff. A member of the research team will accompany the participant back to the inpatient unit.
- g. In the event that the subject needs to leave the scanner while scanning (e.g. to use the bathroom) we will perform an additional low dose CT transmission scan.

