There is evidence of brain atrophy in depression: gray matter volume is reduced in the prefrontal cortex (PFC) and in the hippocampus (HC) in depressed individuals (12). Postmortem studies in depression show low expression of several genes related to synaptic function and decreased synapse number in the dorsolateral PFC (13). Chronic stress, a risk factor for depression, precipitates neuronal atrophy and dendritic spine loss in HC and PFC (14, 15). Preclinical work in rodents suggests that ketamine may exert antidepressant effects by reversing neuronal atrophy, specifically through the formation of new dendritic spine synapses in the brain. In rodents, ketamine induces rapid synaptogenesis via stimulation of mechanistic target of rapamycin (mTOR) and brain-derived neurotrophic factor (BDNF), leading to a reversal of chronic, stress-induced neuronal atrophy (4-7).

A recently developed research tool enables examination of synaptic density *in vivo* in humans. [11C]UCB-J is a PET radiotracer that is specific for synaptic vesicle glycoprotein 2A (SV2A) (16, 17), providing a quantitative measure of synaptic density *in vivo* in the brain in humans. A recent PET imaging pilot study identified low [11C]UCB-J binding in the PFC of individuals with current MDD as compared to healthy volunteers, providing early evidence that this synaptic density biomarker may quantify a disease-relevant process in depression (18). Furthermore, PET imaging with [11C]UCB-J displays outstanding test-retest reliability, with absolute test-retest variability of only 4-5% in brain regions of interest in this study (19), making it an outstanding tool for longitudinal studies of the effects of treatment interventions. We therefore propose to directly quantify synaptic density in depressed patients to investigate whether it is increased by treatment with ketamine in a regionally-specific manner. Moreover, we will examine synaptic density as a mediator of the sustained antidepressant effects of ketamine and as a predictor of treatment outcome. We will quantify synaptic density using PET imaging before and after a course of 4 sequential intravenous infusions of ketamine administered over a two-week period.

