# **Specific Aims and Hypotheses**

Specific Aims and Hypotheses

AIM 1: Quantify changes in regional synaptic density in response to intravenous ketamine. We hypothesize that administration of ketamine in individuals with MDD will induce new spine synapse formation and synaptic protein synthesis, reflected by increased synaptic density in mPFC and HC as quantified by changes in VT derived from PET imaging with [C]UCB-J performed prior to and approximately 24 hours following a course of four ketamine infusions.

AIM 2: Evaluate the relationship between sustained improvement in depressive symptoms in response to intravenous ketamine and change in  $^{11}$ C-UCB-J binding. We hypothesize that the magnitude of the change in  $^{11}$ C-UCB-J VT in mPFC and HC in response to intravenous ketamine administration will correlate with clinical improvement on the Hamilton Depression Rating Scale from baseline to one week following the final ketamine infusion.

AIM 3: Examine whether baseline synaptic density in MDD-relevant brain regions as measured by PET imaging with [C]UCB-J predicts the magnitude of sustained antidepressant effects of intravenous ketamine treatment. Hypothesis: lower pre-treatment [C]UCB-J binding (VT) in mPFC and HC will predict greater improvement in depressive symptoms assessed one week following final ketamine infusion as assessed by the Hamilton Depression Rating Scale. This aim

is based on the assumption that individuals with MDD who have particular deficits in this biological measure (regionally-specific synaptic density) will benefit most from an intervention that acts to restore such deficits.

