# **Description of Subject Population**

### Sample #1

Specify subject population

Depressed adults with current MDD

Number of completers required to accomplish study aims

2.0

Projected number of subjects who will be enrolled to obtain required number of completers

40

Age range of subject population

18-55

Gender, Racial and Ethnic Breakdown

Based on historical recruitment of depressed patients for research studies in our division, we expect the following gender and ethnic breakdown: Male (40%); Female (60%); White (67%); Black (24%); Hispanic (16%); Asian (9%).

Description of subject population

We will recruit unipolar depressed patients in a current major depressive episode. We will attempt to recruit individuals who are unmedicated in the current episode, although this will not be required for study participation. Based on studies in our clinic, subjects come from the 5 boroughs of New York City and the nearby tri-state suburbs.

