### 7. Post-infusion Neuroimaging:

a. PET imaging with [C]UCB-J, performed identically as described above, will be repeated as close to 24-48 hours following the 4th ketamine infusion as is possible with scheduling availability of the PET Center. If participants do not complete all four ketamine infusions for any reason (including adverse effects of ketamine, lack of clinical response and preference not to complete all sessions, etc), we may conduct repeat (post-ketamine) [C]UCB-J PET scan after fewer ketamine administrations.

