# **Blood and other Biological Samples**

Please create or insert a table describing the proposed collection of blood or other biological specimens

Sample	Collection Time Point	Total Collected per Participant
Blood	Baseline (through protocol 4815): 43ml	Maximum blood drawn through both protocols collectively: ≤243ml
	Arterial blood sampling during PET scans, pre- and post-ketamine infusion: ≤100ml x 2 = ≤200 ml	

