### 1B. Radiotracer physiological effects:

Consistent with previous work with [\$^{11}\$C]UCB-J\$ (17), we will limit injected mass to 10 micrograms. The safety of [11C]UCB-J\$ at similar injected masses has been demonstrated in PET studies published in the literature, including 10 healthy volunteers and 3 individuals with epilepsy in this study (17); five of whom received repeat [11C]UCB-J\$ injections and scans the same day (20). Another study performed PET imaging with [\$^{11}\$C]UCB-J\$ on 10 individuals with amnestic mild cognitive impairment and 11 individuals who were cognitively normal (21). The risk of an idiosyncratic reaction is acknowledged in the consent form. A physician will be **available** at the time of each injection of the radiotracer. Any adverse reaction to the radioactive drug (radiation related or not) will be reported to the NYPSI IRB and the JRSC.

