### 1C. Placement of Intra-arterial catheter

Radial arterial catherization is needed for repeated arterial blood samples to construct tracer input curves. Complications resulting from such short-term catheterizations include bleeding, occlusion, clotting, or infection.

The following paragraph appears in the subject consent forms as per the IRB website, with one phrase added [shown here in italics] for more clarity for participants with lack of mathematical skills:

"The placement of a catheter in your artery may cause discomfort. There is a very small chance of complications from this catheter such as bleeding, bruising, infection or blood clot. There is an extremely low risk (0.09%, or about 1 in a thousand) of cutting off circulation to your hand which could result in a need for surgical repair or, in rare instances, could result in the loss of use of part of or all of the hand. These complications are rare and usually occur in medically ill patients who have catheters in their wrists for several days. In contrast, the catheter will remain in your arm for about four hours for this study. If you have a history of a bleeding disorder or are taking certain medications that affect blood clotting, you will not be asked to participate in this study."

The radial artery catheter is placed by an experienced physician.

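### Does the venous-sampling fallback oblige the SAP to specify how participants with one arterial and one venous PET scan are analysed?

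*Combined protocol and SAP*

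**What the plan says.** Study Procedures, 5. Pre-Infusion Research Measures, item e, plans a radial artery catheter for each scan, to measure the input function and the unmetabolized tracer in plasma. Only if that catheter cannot be placed, "we may place a second intravenous catheter and perform venous blood sampling instead of arterial blood sampling". The same item sets its blood-volume limit for both PET scans.

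Study Procedures, 7. Post-infusion Neuroimaging, has the second scan "performed identically as described above, will be repeated as close to 24-48 hours" after the last infusion, so the fallback carries over to it.

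Two other places assume arterial blood. Risks, 1C, states: "Radial arterial catherization is needed for repeated arterial blood samples to construct tracer input curves". The table under Blood and other Biological Samples lists only "Arterial blood sampling during PET scans, pre- and post-ketamine infusion".

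Aim 1 concerns the change in VT. Aim 2 supposes that this change "will correlate with clinical improvement on the Hamilton Depression Rating Scale from baseline to one week following the final ketamine infusion". Aim 3 uses baseline VT. The SAP names linear mixed models, two-sided tests at alpha 0.05, diagnostic plots with review of outliers, and further exploratory analyses. It says nothing on sampling route.

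**The concern.** Risks, 1C, treats arterial blood as necessary for the input curve, yet the procedures allow a substitute without saying how VT is then derived or whether the two scans must match. If VT from venous samples differs systematically from VT from arterial samples, a participant with one of each carries that difference in the change score. The tracer is described as having "absolute test-retest variability of only 4-5% in brain regions of interest", so a route error of around 10% would be large beside ordinary scan-to-scan noise.

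Two things would be at stake. If several switches ran in one direction, the Aim 1 test could mistake a route effect for a ketamine effect or hide a real one. In Aim 2, any switch adds noise to the correlation with Hamilton improvement. The decision to keep or omit such participants would also be taken after the data were seen.

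**Working it through.** The plan gives no power, effect size or SD, so there is no figure of its own to reproduce. What follows shows sensitivity only.

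**Inputs from the documents.** Test-retest variability is 4-5% (Background) and alpha is 0.05 two-sided (SAP). Under Sample #1, "Number of completers required to accomplish study aims" is printed as 2.0, with 40 to be enrolled; 2.0 is read here as 20.

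**Assumed inputs.** The venous error in VT is +5.3% or +11.1%, the true rise is 4%, and the Aim 2 correlation is 0.5. The sign of the venous error is arbitrary; if it were negative, the two directions below would swap.

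**SD of change.** For normal differences with mean zero, SD = variability × √(π/2). This gives 4 × 1.253 = 5.0% and 5 × 1.253 = 6.3%. A value of 10% is added in case variability over the treatment interval is larger.

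**Shift in the mean.** On the log scale an error of +11.1% is 0.105. With k of 20 pairs switching the same way, the mean change moves by k × 0.105 / 20. That is 0.5 points for one pair and 2.1 points for four.

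**Aim 1, 20 pairs, error +11.1%, route ignored unless stated**

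| Case | SD 5.0 | SD 6.3 | SD 10 |
|---|---|---|---|
| Type I error, 4 pairs arterial then venous | 0.21 | 0.17 | 0.11 |
| Type I error, 1 pair, or 4 in random direction | 0.05 | 0.05 | 0.05 |
| Power, no mixed pair | 0.91 | 0.75 | 0.38 |
| Power, 1 pair venous then arterial | 0.76 | 0.58 | 0.29 |
| Power, 4 pairs in random direction | 0.67 | 0.56 | 0.33 |
| Power, 4 mixed pairs omitted | 0.83 | 0.64 | 0.31 |

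The worst cell is four pairs all venous then arterial, where power at SD 5.0 falls to 0.15. At +5.3% the effects are smaller: type I error is 0.11 / 0.09 / 0.07 with four one-way pairs, and power is 0.86 / 0.70 / 0.37 with four in random direction.

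**Aim 2.** Power is 0.64 with no mixed pair. At +11.1% it is 0.54 / 0.57 / 0.61 with one mixed pair and 0.35 / 0.43 / 0.53 with four in random direction.

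**Aim 3.** Starting again from about 0.64, four venous baselines at +11.1% leave power at 0.55-0.62.

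**Pairs venous at both scans.** Type I error stays at 0.05 and power is unchanged, provided the venous error is a stable proportion.

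**What the obvious remedy costs.** If one mixed pair occurs and the analyst omits it, the noncentrality for Aim 1 at SD 5.0 goes from 3.92 × √20 / 5.01 = 3.50 (19 df) to 3.92 × √19 / 5.01 = 3.41 (18 df). Power goes from 0.91 to 0.90. A route term in the model does the same thing. With k mixed pairs and S the sum of route differences, the variance of the estimated change is SD² × k / (nk − S²). For k = 1 that is SD² / 19 on 18 df, identical to omission.

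**What the SAP's diagnostics would show.** For a single mixed pair at +11.1%, a studentized residual beyond 3 appears in 21 / 12 / 4% of trials, and beyond 2 in 53 / 38 / 19%. The check helps but is not a dependable detector.

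**The case for a change.** The best case for changing the plan is that every factual part of the concern is true. The fallback is open at either scan, and asking for an identical repeat cannot secure a match when placement fails only once. The SAP is silent, and its outlier review would usually miss a single moderate mismatch at a cutoff of 3. One mixed pair in the unfavourable direction costs Aim 1 about 0.15 in power at SD 5.0 (0.91 to 0.76). A line in the SAP would cost almost nothing and would settle the handling before results are known.

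The facts and the arithmetic stand. What does not follow is that the plan is deficient without that line. The documents give no frequency for failed placement and no size or direction for a venous error, so even one mixed pair is an assumption, and the large figures need four in 20. The route need not be discovered through residuals, because the team must know which blood it has in order to build the input function. Any wording would add a sensitivity analysis that runs only if a mixed pair turns up and would leave the primary analysis alone. In the likeliest version of the problem, a single pair, analysts would reach the same two results unprompted: with the pair and without it.

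**Conclusion.** No change to the plan is needed. The SAP leaves a detail unstated, and analysts can fill it sensibly by noting the route of each scan and, if a participant's routes differ, reporting the VT-change result with and without that participant. Omitting one such pair costs about 0.01 in Aim 1 power under the inputs above. The fallback is also a fair trade-off, since it lets a scan go ahead with blood data when the arterial line fails.

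The possible harm ranges from nothing, if no mixed pair occurs, to a type I error of about 0.21 or a power of 0.15 with four one-way pairs in 20 at +11.1% and SD 5.0. All of this rests on assumed values for the number of completers, the venous error, the true change and the number of mixed pairs. Effects on Aims 2 and 3 weigh less: the lay summary places the mediator and predictor questions among exploratory analyses, and the SAP calls the study a pilot, though it does not list which aims are primary. The conclusion would deserve another look if several mixed-route pairs accumulated, mostly in one direction.
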